2.0 Goals

2.1 Primary

2.11 Determine the rate of MRD-negative responses (in both blood and bone marrow) at any time during treatment with ibrutinib maintenance.

2.2 Secondary

2.21 Median time to achieve MRD⁻ (negative) status (in blood and in bone marrow) after initiation of ibrutinib maintenance treatment.

2.22 Toxicity profile of ibrutinib as maintenance therapy after frontline induction.

2.23 Durability of the MRD⁻ state (determined from the time of first documentation of MRD⁻ until the first documentation of MRD⁺ (or last date shown to be MRD- for a censor)).

2.24 Time to requirement of next therapy for patients who achieve confirmed MRD⁻ vs. those who remain MRD⁺ disease at 48 weeks (end of 12 cycles).

2.25 Progression free survival (as determined by the IWCLL criteria) among patients who achieve confirmed MRD vs. those who remain MRD⁺ disease at 48 weeks (end of 12 cycles).

2.3 Correlative Research

2.31 To conduct correlative studies for further understanding of the mechanism of antitumor activity of ibrutinib in eradication of the MRD.

2.32 Determine the impact of ibrutinib on depression and anxiety symptoms to better understand toxicity profile of ibrutinib maintenance.

2.33 Determine impact of social support or lack thereof on mood symptoms in CLL patients receiving maintenance treatment.

3.0 Patient Eligibility

3.1 Inclusion Criteria

- 3.11 Understand and voluntarily sign an informed consent form.
- 3.12 Age \geq 18 years.
- 3.13 Able to adhere to the study visit schedule and other protocol requirements including willing to provide blood, baseline bone marrow aspirate, and control DNA samples for correlative research purposes (see Sections 6.2, 4.0, 14.0, and 17.0).
- 3.14 Diagnosis of B-CLL, confirmed by flow cytometry and as per the criteria outlined by the IWCLL/Hallek December 2008 (Refer to Appendix III).
- 3.15 Prior frontline therapy for B-CLL must have been discontinued \geq 56 days but \leq 365 days prior to registration. **NOTE:** Patients on supportive care therapy due to use of specific induction regimen such as antibiotics may continue on those treatments at the discretion of the treating physician.
- 3.16 Patient must have completed a frontline induction therapy (minimum of 2 treatment cycles). **NOTE:** Standard Therapies / therapeutic agents are defined as those listed in the NCCN guidelines for treatment of CLL (nccn.org). Also, patients who received induction regimen as part of a clinical trial and is not necessarily mentioned in the NCCN guidelines, will also be eligible as long as the patient has completed at least 2 treatment cycles of induction regimen, achieved a clinical response (PR or CR) and is able to meet all other criteria for the study. However, patients who have previously received ibrutinib or have been randomized to ibrutinib containing arms in a clinical trial will not be eligible for this study.
- 3.17 Patients must have a sustained clinical response (PR, nPR, CCR, CRi, CR) with documented residual disease (\geq 1 CLL cell per 10,000 leukocytes or \geq 0.01% MRD) either in the blood, bone marrow or a lymph node \geq 3.5 cm by any available techniques.
- 3.18 ECOG performance status of 0, 1 or 2 at registration (see Appendix I).
- 3.19 The following laboratory values obtained \leq 14 days prior to registration:
 - Absolute neutrophil count \geq 1000/mm³
 - Platelet count \geq 30,000/mm³
 - Serum creatinine \leq 1.5 x ULN.
 - Total bilirubin \leq 1.5 mg/dL or direct bilirubin \leq 1.0 mg/dL for patients with Gilbert's syndrome
 - SGOT (AST) and SGPT (ALT) \leq 3.5 x ULN
- 3.19a Negative pregnancy test done \leq 7 days prior to registration, for women of childbearing potential only.

3.2 Exclusion Criteria

3.21 Any serious medical condition, laboratory abnormality, or psychiatric illness that would prevent the subject from signing the informed consent form.

3.22 Since this study involves an investigational agent whose genotoxic, mutagenic and teratogenic effects on the developing fetus and newborn are unknown, any of the following will deem the subject ineligible for the study:

- Pregnant women
- Nursing women
- Men or women of childbearing potential who are unwilling to employ adequate contraception

3.23 Any condition, including the presence of laboratory abnormalities, which places the subject at unacceptable risk if he/she were to participate in the study or confounds the ability to interpret data from the study.

3.24 Use of any other experimental drug or therapy \leq 28 days prior to registration on this study. NOTE: Patients on low dose prednisone (\leq 10 mg) for treatment of conditions other than CLL are eligible.

3.25 Patients who have received more than 1 prior therapy. NOTE: (Prior therapy is defined as any single agent or combination regimen that is included as treatment for symptomatic CLL. Treatment(s) given prior to the symptomatic phase of the disease (preventive strategy) will not be considered as prior induction therapy. For the purpose of a particular therapy/regimen to be counted towards the number of prior treatments a patient must have received at least 2 cycles of the induction regimen e.g., a patient who change their treatment regimen after only 1 cycle (due to toxicity or any other reason) will not be considered to have "2" prior therapies.

3.26 Patients who have progressive disease or relapse (as defined by the IWCLL criteria see Section 11.23) at or any time before registration on this study.

3.27 . No other prior malignancy is allowed except for the following: adequately treated basal cell or squamous cell skin cancer, *in situ* cervical cancer or any other cancer *in situ*, adequately treated Stage I or II cancer from which the patient is currently in complete remission, or any other cancer from which the patient has been disease free for three years.

3.28 Patients who are already MRD⁻ (both in the blood and the bone marrow) after frontline therapy and have lymph nodes $<3.5\text{cm}$.

3.29a Concomitant use of warfarin or other Vitamin K antagonists [see Section 9.5(d)].

3.29b Requires treatment with a strong cytochrome P450 modulators (CYP3A inhibitor and/or CYP3A inducers) [see Section 9.5(a)]. NOTE: A comprehensive list of inhibitors, inducers, and substrates may be found at <http://medicine.iupui.edu/clinpharm/ddis/main-table/>. This website is continually revised and should be checked frequently for updates.

3.29c Currently active, clinically significant hepatic impairment Child-Pugh class B or C according to the Child Pugh classification (see Appendix VII)

- 3.29d Major surgery \leq 4 weeks prior to registration.
- 3.29e Patients who have active infectious hepatitis.
- 3.29f Patients with other diseases that in the opinion of the treating physician pose a higher risk for treatment with ibrutinib therapy including active HIV infection and bleeding disorders.

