
In this clinical trial we will prospectively evaluate these questions. The design of this clinical trial allows enrollment of all patients who have completed their initial induction regimen independent of the type of regimen (therapy) given to them as long as they are MRD⁺. Thus this study will be able to determine prospectively if attainment of MRD⁻ post-induction can potentially be possible with the novel agent ibrutinib given in a *primary* maintenance setting. Thus this study is unique in the following manner (a) it will evaluate the role of single agent ibrutinib in eradication of MRD (b) it will evaluate whether the attainment of MRD negativity is possible with ibrutinib and is it independent of the frontline therapy given (c) the role and benefit of continuous therapy independent of attainment of MRD negativity and the impact of this in durability of MRD⁻ status.

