11.1 Overall Schedule of evaluations

(a) **Clinical Response:** Will be evaluated and documented at baseline (this is defined as the response to the induction therapy). Thereafter clinical response will be evaluated for progression of disease only every 3 cycles of study treatment (for 36 cycles) and every cycle (every 3 months) during follow-up period of without therapy for 2 years.

(b) **MRD status:** To be assessed at baseline (document positivity in blood or bone marrow) and then every 3 cycles of treatment (for 36 cycles) and thereafter every 3 months (for MRD-) and every 6 months (for MRD+) during follow-up without therapy for 2 years.

Note: Bone marrow aspirate done solely for MRD will be considered research. As outlined by the IWCLL guidelines a bone marrow biopsy / aspirate is required to document complete remission. Thus, a bone marrow biopsy / aspirate that is done as part of the clinical response to therapy (such as to document complete remission as part of clinical care as required by the IWCLL guidelines) will be considered standard of care. Additionally, if the bone marrow biopsy or aspirate is done as part of the clinical care of the patient (as determined by the treating physician) that procedure will be considered standard of care.

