16.0 Statistical Considerations and Methodology

16.1 Overview:

This is a Phase II study designed to assess the eradication of minimal residual disease (MRD) as well as the toxicity associated with ibrutinib used as maintenance therapy in CLL patients who achieve a PR, nPR, CCR, CRi, or CR post-induction therapy but who have residual disease (i.e. MRD positive).

16.11 Primary Endpoint:

The primary endpoint of this trial is the rate of confirmed MRD-negative response at any time during treatment with ibrutinib maintenance. A confirmed MRD-negative response is defined as an achievement of MRD-negative status in both the blood and the bone marrow on two consecutive evaluations at least three months apart. Confirmed MRD-negative response will be evaluated using all cycles of treatment. Throughout Section 16.0, confirmed MRD-negative response will be considered synonymous with "success" unless specified otherwise. All patients meeting the eligibility criteria who have signed a consent form and have begun treatment will be evaluable for confirmed MRD-negative response, with the exception of patients who are determined to be a major treatment schedule violation.

16.2 Statistical Design:

16.21 Decision Rule:

Prior clinical investigations have evaluated eradication of the MRD with consolidation treatment post induction therapy and these suggest the importance of MRD eradication after first-line therapy. None of these studies have investigated primary maintenance after first-line induction treatment. Two ongoing studies (mentioned in the introduction) have been initiated, but no data is available. Therefore, any indication of benefit with ibrutinib maintenance therapy will be considered promising.

The largest success proportion where the proposed treatment regimen would be considered ineffective in this population is 5%, representing a response by chance alone. The smallest success proportion that would warrant subsequent studies with the proposed regimen in this patient population is 20%. The following one-stage binomial design uses 32 evaluable patients to test the null

hypothesis that the true success proportion in a given patient population is at most 5%.

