The analysis for this trial will commence at planned time points (see 16.2) and at the time the patients have become evaluable for the primary endpoint. Such a decision will be made by the Statistician and Study Chair in accordance with CCS Standard Operating Procedures, availability of data for secondary endpoints (e.g., laboratory correlates), and the level of data maturity. It is anticipated that the earliest date in which the results will

be made available via manuscript, abstract, or presentation format is when the last patient has been followed for at least 6 months.

16.31 Primary Endpoint:

- 16.311 Definition: The primary endpoint of this trial is the rate of confirmed MRD-negative response. A confirmed MRD-negative response is defined as an achievement of MRD-negative status in both the blood and the bone marrow on two consecutive evaluations at least 3 months apart. Confirmed MRD-negative response will be evaluated using all cycles of treatment. All patients meeting the eligibility criteria who have signed a consent form and have begun treatment will be evaluable for response, with the exception of patients who are determined to be a major treatment schedule violation.
- 16.312 Estimation: The proportion of successes will be estimated by the number of successes divided by the total number of evaluable patients. Ninety-five percent exact binomial confidence intervals for the true success proportion will be calculated.

16.32 Secondary Endpoint:

- 16.321 Duration of MRD-negative response is defined in patients who have achieved a confirmed MRD-negative response as the time from the earliest date that the patient was noted as having MRD-negative response in both the blood and bone marrow until the first notation of MRD positive disease in the blood or the bone marrow. The distribution of duration of MRD-negative response will be estimated using the method of Kaplan-Meier.⁵⁸
- 16.322 Time to MRD-negative response is defined in patients who have achieved a confirmed MRD-negative response as the time from the date of registration to the earliest date that the patient was noted as having MRD-negative response in both the blood and bone marrow. Time to MRD-negative response will be summarized descriptively (median, range).

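### A patient already MRD-negative in blood and marrow can enrol on a lymph node of at least 3.5 cm and be counted as a success for staying negative

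*Combined protocol and SAP*

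**What the plan says.** **Eligibility.** Inclusion 3.17 requires a sustained clinical response with documented residual disease (0.01% or more) "either in the blood, bone marrow or a lymph node" of at least 3.5 cm. Exclusion 3.28 is the mirror image. It removes patients who are MRD-negative "both in the blood and the bone marrow) after frontline therapy and have lymph nodes" smaller than 3.5 cm.

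**Endpoint.** Section 11.3 defines MRD-negative by the CLL cell fraction in blood or marrow; nodes play no part. Sections 16.11 and 16.311 define success as MRD-negative status in both blood and marrow on two consecutive evaluations at least three months apart. On evaluability, 16.11 states: "All patients meeting the eligibility criteria who have signed a consent form and have begun treatment will be evaluable for confirmed MRD-negative response". Section 16.311 repeats that they "will be evaluable for response, with the exception of patients who are determined to be a major treatment schedule violation".

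**Text that assumes positivity at entry.** Section 1.3 describes enrolment whatever regimen was "given to them as long as they are MRD"-positive. Section 11.1(b) says of MRD status: "To be assessed at baseline (document positivity in blood or bone marrow"). Section 16.1 describes responders to induction "but who have residual disease (i.e. MRD positive"). Section 16.21 sets the null success proportion at 5%, "representing a response by chance alone".

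**Decision rule.** Under 16.211, 4 or more successes in 32 evaluable patients is evidence of promising activity; 3 or fewer is not.

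**The concern.** The trial asks whether ibrutinib turns MRD-positive patients MRD-negative. A patient who enters negative in both compartments cannot answer that question, yet the written rule can score that patient as a success for not changing. The 5% null does not describe such a patient, who already meets the MRD-negative definition on day one.

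Because the rule turns on four events, one such success can decide the result. The literal evaluability rule counts the patient, while the descriptive text in 1.3, 11.1(b) and 16.1 suggests otherwise. If one enrols, which text governs could be argued in an open single-arm trial once results are known.

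The secondary endpoints are affected too. Time to MRD-negative response (16.322) runs from registration and has no meaning for someone negative at registration. Duration (16.321) would include negativity produced by induction rather than by maintenance.

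**Working it through.** **Step 1: does the route exist?** By 3.17, residual disease may be in blood, or marrow, or a node of at least 3.5 cm. By 3.28, a patient negative in blood and marrow is excluded only if nodes are also below 3.5 cm. Negative blood, negative marrow and a node of at least 3.5 cm passes both. If 3.17 is read as requiring MRD to be shown within the node, blood and marrow may still both be negative.

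**Step 2: does anything later close it?** Sections 11.3, 16.11 and 16.311 look only at blood and marrow during treatment. The only stated exception to evaluability is a major treatment schedule violation. No baseline condition appears.

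**Step 3: reproduce the plan's figures.** Inputs: n = 32, cut-off 4 (16.211), null 0.05 and target 0.20 (16.21). The formula is P(Bin(32, p) ≥ 4).

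| True proportion | Plan (16.24) | Recomputed |
|---|---|---|
| 0.05 | 0.07 | 0.0738 |
| 0.10 | 0.40 | 0.3997 |
| 0.15 | 0.73 | 0.7279 |
| 0.20 | 0.91 | 0.9069 |

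The plan's table is correct for its stated model.

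**Step 4: add patients negative at entry.** Let k of the 32 be negative in both compartments at entry, each with probability q of meeting the success definition without any drug effect. The other 32 − k succeed with probability 0.05. The documents give neither k nor q, so a range is shown.

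P(promising) = P(J + Bin(32 − k, 0.05) ≥ 4), with J ~ Bin(k, q).

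For k = 1 this is (1 − q) × P(Bin(31, 0.05) ≥ 4) + q × P(Bin(31, 0.05) ≥ 3) = (1 − q) × 0.0671 + q × 0.2008. At q = 0.2: 0.8 × 0.0671 + 0.2 × 0.2008 = 0.094.

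| k | q = 0.2 | q = 0.5 | q = 1 |
|---|---|---|---|
| 0 | 0.074 | 0.074 | 0.074 |
| 1 | 0.094 | 0.134 | 0.201 |
| 2 | 0.117 | 0.221 | 0.447 |
| 3 | 0.143 | 0.330 | 0.774 |

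**Step 5: effect on the estimate.** The expected proportion is (kq + (32 − k) × 0.05) / 32. For k = 2 it is (0.4 + 1.5)/32 = 5.9%, (1.0 + 1.5)/32 = 7.8% or (2.0 + 1.5)/32 = 10.9%, against 5.0% for k = 0.

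**Step 6: a single-patient illustration.** With four successes, one of them negative at entry, the report reads 4/32 = 12.5% (exact 95% CI 3.5% to 29.0%) and the regimen is promising. Without that patient the data are 3/31 = 9.7% (2.0% to 25.8%), with three successes rather than four.

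**The case against.** The best defence is that the intent is clear. Section 16.1 equates residual disease with MRD positivity, 16.21 applies its rates to that population, and the endpoint speaks of achieving a response, which suggests conversion. Section 11.3(A) also calls for a baseline aspirate to document MRD-positive status. (Its note says positive blood both removes and triggers the need for marrow; the second instance looks like a slip for negative.) This is good evidence of intent, but none of it is an eligibility criterion, evaluability rule or success rule, and 3.17 and 3.28 deliberately provide the node route using one shared threshold.

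The size is also assumed, and this stands. Such patients may be few: 3.17 requires a sustained response, and under Appendix XII a palpable node of this size does not fit CR, CCR or nPR, which leaves mainly PR patients or nodes seen only on CT. Success is not automatic either. The patient must stay on treatment and test negative repeatedly, and drug-related lymphocytosis could turn blood positive, although 9.4 says it is unknown whether this happens after induction. The q = 1 column is therefore an upper bound.

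The 4/32 against 3/31 comparison is only an illustration. The cut-off was set for 32, and a replacement patient's outcome would be unknown. Sections 16.211 and 16.25 also leave some judgement in the decision. These points limit the weight of the concern; they do not supply the missing rule.

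**Conclusion.** The concern holds. As written, the plan admits patients who are MRD-negative in blood and marrow and allows them to count as primary-endpoint successes for remaining so. This contradicts the plan's own description of its population and the meaning of its null. If no such patient enrols, nothing changes and the false-positive probability stays at 0.074. One such patient raises it to between 0.094 and 0.201, and two to between 0.117 and 0.447, for q from 0.2 to 1 with all other patients at the 5% null. The textual gap is certain; its numerical effect rests on assumed k and q. It should be fixed because it touches the primary decision and is cheap to close.

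**What to change.** In 16.11 and 16.311, limit the primary evaluable set and the 4-of-32 rule to patients with documented baseline MRD of at least 0.01% in blood or bone marrow, by any method the protocol accepts, including a qualifying post-induction marrow under footnote 10 of the Test Schedule. State whether a footnote 10 marrow reported as residual disease without a quantified MRD level qualifies. Define success as conversion from that baseline state. Report patients enrolled only on a node of at least 3.5 cm separately, for safety and progression-free survival. Reconcile 3.17 and 3.28 with 1.3, 11.1(b) and 16.1. Eligibility itself need not change.

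The cost is one sentence in each of two sections plus the wording reconciliation. No new test is needed: footnote 8 already requires baseline blood MRD for everyone and marrow MRD when blood is negative.

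The downside is that node-only patients must be replaced, and the 3 extra places in 16.22 also have to cover ineligibility, cancellation and major violations. With full replacement, alpha and power stay at 0.074 and 0.907. Without replacement, keeping the cut-off at 4:

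| Evaluable n | Alpha at 5% | Power at 20% |
|---|---|---|
| 32 | 0.074 | 0.907 |
| 31 | 0.067 | 0.893 |
| 30 | 0.061 | 0.877 |
| 28 | 0.049 | 0.840 |

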4.0 Test Schedule

All visits \pm 4 days unless otherwise stated.

| Tests & Procedures | Active Monitoring Phase | | | | | |
|---|----------------------------|-----------------|---------------|---|----------------------------|-------------|
| | Days Prior to Registration | \leq 14 days | Cycle 1 (Pre) | Prior to subsequent Cycles 2-36 | Study Drug Discontinuation | Observation |
| | | | | 3-4 weeks from the last day of the last cycle | | |
| Complete medical history (including prior treatment regimen) | X | | | | | |
| Adverse event assessment | X | | | X | X | X |
| Physical exam, including weight and vital signs, and PS ¹ | | X | X | X ²⁰ | X | X |
| Clinical Response assessment (Tumor measurement by physical exam) ^{2, 3} | | X | | X | X | X |
| CT scans (Chest, Abdomen, Pelvis) ⁴ | X | | | | X | |
| EKG/ECHO ⁵ | X | | | | | |
| CBC with differential ⁶ | | X | X | X | X | X |
| Chemistry group (SGOT [AST], SGPT [ALT], serum creatinine, total bilirubin, LDH, uric acid, phosphorus, alkaline phosphate, serum electrolytes) ⁶ | | X | X | X | X | X |
| Direct bilirubin ¹⁵ | | X | | | | |
| Quantitative Immunoglobulins | X | | | X ⁷ | X | |
| Quantitative T & B cells, peripheral blood | | X | | X ¹⁷ | | |
| Minimal residual disease assessment ⁸ | X | | | X | X | X |
| Flow Cytometry-CLL Panel ⁹ | X | | | | | |
| Bone marrow biopsy and/or aspirate ¹⁰ | X | | | X | X | X |
| CLL FISH Panel ¹¹ , | X | | | | | |
| Zap 70, CD38, IgHV ¹² | X | | | | | |
| Beta 2 microglobulin ¹² | X | | | | | |
| Research blood sample collection ^{13, R} | | X | | X | X | X |
| Research bone marrow aspirate collection ^{14, R} | X | | | X | X | X |
| Mandatory DNA sample which can be collected from any one of the 3 sources (buccal swab, skin biopsy or myeloid cells from bone marrow) as noted in Section 17.0 | | X ¹⁸ | | | | |
| Urine Pregnancy test | | X ¹⁶ | | | | |
| PHQ-8; GAD; Living Situation; MOS-SSS-4 Question; QOL | | X | | X ¹⁹ | | |

1. During the first 2 cycles of treatment, patients will have a focused clinical examination weekly, as necessary, for the monitoring of tumor lysis syndrome (TLS). This can be done in collaboration with local MD/referring physician.
2. The physical exam should measure the spleen and liver, noting the maximal distance below the respective costal margins and should record the bi-dimensional diameter of the largest palpable node in each area of involvement including the following sites: left neck (sub-mandibular, cervical, supra-clavicular), right neck (sub-mandibular, cervical, supra-clavicular), left axillary, right axillary, left groin (inguinal, femoral) and right groin (inguinal, femoral).
3. Clinical response assessment: will be done per IWCLL criteria starting with evaluation of disease state at baseline and for progression of disease only every 3 cycles (for 36 cycles) during study treatment and every cycle (every 3 months) during follow-up without therapy.
4. CT scans should be done as clinically indicated for the management of the patient and in accordance with the IWCLL guidelines. CT scans may be done with patient's primary physician (if outside Mayo Clinic), results of these will be entered in the source document.
5. EKG or ECHO only if clinically indicated.
6. Hematology (CBC) / Serum Chemistry: During cycle 1 and 2, day 8 and 15 labs will be done at the treating physician discretion based on patient's clinical needs and/or can be done based on risk for TLS or for conduct of correlative studies. Monitoring for TLS is considered standard of care. In subsequent cycles CBC/chemistry will be done prior to beginning of each cycle as standard of care and additional testing will only be done as clinically indicated to be determined by treating physician. Laboratory workup may be done with patient's primary physician (if outside Mayo Clinic), results of these will be entered in the source document.
7. Quantitative immunoglobulin will be done at baseline and thereafter can be done every 4 cycles at the discretion of the treating physician and as per standard clinical practice.
8. Minimal residual disease: MRD assessment will be done at baseline, during the treatment phase and then during the observation phase (no treatment). The MRD will be done on peripheral blood and / or bone marrow aspirate using flow cytometry standardized Mayo Clinic panel. In general bone marrow aspirate evaluation will only be required when the peripheral blood is recorded at least twice (at two separate evaluation 3 months apart) to be negative. If blood is positive for MRD assessment, then bone marrow aspirate evaluation for the MRD will not be needed and can be deferred. **MRD assessment in the Blood:** (a) **Baseline:** all patients will have MRD assessed in the peripheral blood prior to initiating the study. (b) **During treatment phase:** all patients will have MRD assessed in the peripheral blood every 3 cycles. If the ibrutinib maintenance treatment is held > 21 days for toxicity or for any other reason(s) then the MRD testing will be delayed to accommodate 3 treatment cycles prior to testing. (c) **During observation period:** all patients will have MRD assessed within 4 weeks of completion of the last treatment cycles and thereafter every 3 months (if they are MRD negative) and every 6 months (if they are MRD+) for a maximum follow-up of 2 years or until initiation of subsequent treatment for relapsed disease (whichever happens first). **MRD assessment in the Bone marrow aspirate:** The schedule of assessment of the bone marrow aspirate for MRD will be different and dependent upon the results of the MRD status in the blood. (a) **Baseline:** If the peripheral blood MRD results are positive then a BM aspirate assessment for MRD will not be needed. If the peripheral blood MRD results are negative, then a BM aspirate assessment for MRD will be needed. (b) **During the treatment phase:** The MRD assessment of the Bone marrow aspirate will only be required once the peripheral blood MRD is recorded to be negative for at least 2 evaluations that are separated at least 3 months apart. If the blood evaluation demonstrates positivity for MRD, then Bone marrow aspirate evaluation will not be required and can be deferred until the peripheral blood is noted to be negative x 2. (c) **During the observation period:** The MRD assessment of the Bone marrow aspirate will only be required if the post treatment peripheral blood assessment (i.e., that done within 4 weeks of the last treatment dose) was noted to be negative. If the post treatment blood evaluation was noted to be positive, then no bone

marrow aspirate evaluation is required. It is possible, though unlikely, that during observation period the peripheral blood (evaluated every 3 months) may convert to negative. If this is observed, then a bone marrow aspirate for MRD will be done only if 2 consecutive blood MRD assessments are recorded to be negative. **Note:** Bone marrow aspirate done solely for MRD will be considered research, however if the procedure is done to assess response to therapy (such as to document complete remission as part of clinical care as required by the IWCLL guidelines) then it will be considered standard of care.

- See detailed section on the MRD (see Section 11.4).

9. Flow cytometry-CLL Panel: The objective of this is to confirm diagnosis as per standard of care (pretreatment). Patients who have a flow cytometry done at any time prior to starting the clinical trial which validates the diagnosis of B-CLL will not be required to have it repeated.
10. **Bone marrow biopsy/aspirate:** At baseline documentation of bone marrow assessment (aspirate and biopsy) will be required to determine the extent of marrow involvement and / or confirmation of presence of MRD. This is standard of care as per the IWCLL guidelines to accurately assess response to treatment. The BM assessment (aspirate and biopsy) will not be required if (1) a bone marrow assessment (aspirate and biopsy) was done post induction treatment and this showed residual disease (or MRD positivity) or (2) if a bone marrow post induction was done (with negative disease, or if there was no MRD information) but the peripheral blood at the time of screening show MRD positivity. If no bone marrow aspirate/biopsy is done post induction therapy, then a bone marrow aspirate and biopsy will be required prior to starting maintenance therapy to assess extent of disease in the marrow and establish appropriate response category post induction (this is consistent with the IWCLL guidelines and is standard of care). During the treatment and observation phase, a repeat bone marrow biopsy will only be required to establish the response of complete remission as recommended by the IWCLL guidelines and this will be at the discretion of the treating physician who will determine the appropriate timing based on clinical response assessment (this is consistent with the IWCLL guidelines and is standard of care). Bone marrow aspirate will be done for assessment of MRD and the timing of this will be followed as noted in detail in foot note 8.
11. FISH (*florescent in situ hybridization*) in blood or bone marrow (if no CLL cells in the blood): May be performed any time prior to initiation of therapy. If already done previously (prior to initial induction therapy), the results will be obtained and recorded, repeat testing will not be needed unless clinically indicated and at the discretion of the treating physician.
12. These tests may be performed any time prior to initiation of therapy. If already done previously (prior to initial induction therapy), the results will be obtained and recorded, repeat testing will not be needed unless clinically indicated and at the discretion of the treating physician.
13. For blood collected for correlative studies, see Section 14.0. Samples will be collected at baseline (pre-treatment), prior to cycle 4, prior to cycle 7, prior to cycle 13 and at time of relapse.
14. Bone marrow aspirate (optional) for correlative studies, see Section 14.0. Samples will be collected only if bone marrow biopsy or aspirate is done as part of routine clinical care of the patient (as outlined in footnote 10) or as part of MRD assessment (as noted in footnote 8).
15. Only for patients with Gilbert's syndrome and the total bilirubin >1.5 mg/dL.
16. For women of childbearing potential only. Must be done ≤ 7 days prior to registration.
17. Should be performed after 3 cycles, 6 cycles, 12 cycles, and at time of relapse.
18. Buccal swab may be collected any time prior to starting treatment. Skin biopsy is only required if DNA cannot be obtained from the buccal swab. Alternate source could be myeloid cells in the marrow (in cases where bone marrow is obtained). This will be at the discretion of the treating physician in consultation with the PI.

19. PHQ-8, GAD-7, Living situation, MOS-SSS-4 Question, and Linear Analogue Self-Assessment: Prior to cycle 4, prior to cycle 7, prior to cycle 13, at time of relapse and thereafter every 3 months x4.
20. After the first 6 cycles, clinical evaluation and blood tests can be obtained per test schedule and mailed/faxed to Mayo Clinic and patient can return at least every 3 cycles for follow up to Mayo. Patient may be seen more frequently, if clinically necessary. NOTE: All forms, including AEs, will need to be filled out every 28 days.

R. Research funded.

